
Furthermore, our expectation is that this difference will be most apparent at 48 hrs. as discussed above with a reduction in narcotic requirements greater than 40% in the continuous catheter TAP group vs. standard single shot Bupivacaine TAP (4.1 mg +/- 3 mg vs. 2.4 mg +/- 1.3 mg Dilaudid). This is based on the assumption that the effects of the local anesthetic control TAP (single shot Bupivacaine) may last up to 24 hrs. At 72 hrs, prior studies, although limited, have not shown a significant difference between TAP block and placebo groups.

c Study Objectives

Primary Aim

The primary aim is to evaluate for any significant difference total post-operative narcotic requirements (Dilaudid) required over 48 hrs. in the continuous catheter TAP block arm vs. the single shot Bupivacaine TAP arm and again the slow release Liposomal Exparel® TAP arm vs. the single shot Bupivacaine TAP arm.

Secondary Aim

The secondary aim will be to evaluate for any significant difference in narcotic requirements at other endpoints such as 24 hrs and at 72 hrs. As discussed before, current studies do not show a significant difference when extrapolated out at those end points, albeit there is very little data at 72 hrs. Other quality indicators of recovery in the three arms such as Visual Analog Scores (VAS) are expected again to be most significantly different at 48 hrs. Other quality measures that will be recorded include incidence and severity of post-operative nausea and vomiting (PONV), time to ambulation, and patient satisfaction with post-operative pain control.

Rationale for the Selection of Outcome Measures

Outcome measurements are based on the assumption that narcotic requirements (i.e. intravenous Dilaudid Patient-Controlled Analgesia [PCA] use) are inversely related to patient satisfaction in regards to their post-operative pain. Additional factors such as VAS, ambulation, performance of daily activities, and anti-emetic pharmaceutical requirements have been chosen as quality indicators in regards to post-operative pain control and dependence on narcotics.

D Investigational Agent

This investigation will use three FDA-approved techniques:

- Bilateral Continuous TAP block via Catheter (One-time bolus of Bupivacaine 0.25% x 20ml per side followed by continuous infusion of Ropivacaine 0.2% 7 ml/hr. per side x 48 hrs.);
- Single Injection TAP block with Exparel® (One-time bolus of Bupivacaine 0.25% x 20 ml followed by Exparel 133 mg per side); and

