- Single Injection TAP block with Bupivacaine 0.25% (25 ml-30 ml volume one-time bolus per side).

E Study Design

Overview or Design Summary

It is the purpose of this study to evaluate the efficacy of continuous TAP block via catheter versus single shot Bupivacaine TAP block and also to evaluate the efficacy of slow release Exparel® versus single shot Bupivacaine. The study shall consist of three (3) arms of which patients will be randomly assigned: Bilateral Continuous TAP block via Catheter (One time bolus of Bupivacaine 0.25% x 20 ml per side followed by continuous infusion of Ropivacaine 0.2% 7 ml/hr. per side x 48 hrs); Single Injection TAP block with Exparel® (One time bolus of Bupivacaine 0.25% x 20 ml followed by Exparel 133 mg per side); and Single Injection TAP block with Bupivacaine 0.25% (25-30 ml volume one time bolus per side). Several parameters will be measured with the primary goal being to determine the effectiveness and duration of post-operative pain relief of the newer techniques of extending TAP block duration with the current, commonly used standard single shot Bupivacaine technique. Because a goal of this study is to determine which technique of TAP block is most effective for post-operative pain control, the three (3) arms of this study will be performed in a manner that is most consistent and common with current anesthesia practice. Because TAP block is typically most effective for lower and mid-abdominal incisional pain relief, the nature and height of the incision with regard to the umbilicus will also be recorded.

Parameters Measured:

- 1) Total Post-operative Narcotic Requirements over at 24, 48 and 72hrs.
- 2) Days of IV PCA use: Time to 1st dose, total IV PCA requirements, POD# 0, 1, 2, & 3, additional narcotic use and additional adjuvants
- 3) PACU narcotic requirements
- 4) Pain Score:0-10 on post-operative day (POD)# 0, POD #1, POD #2, POD #3 (am, pm, Max Pain score per day, Pain score at rest, and Pain score with activity)
- 5) Day to Ambulation: O=out of bed assisted/unassisted, W= walk with/without assistance

- 6) Day of Foley removal
- 7) Day of first Bowel Movement
- 8) Anti-emetic Drug (Zofran) requirements.
- 9) Surgical Incisional height in relation to umbilicus or Type of Surgery (recorded by anesthesiologist)
- 10) Anesthesia provider placing TAP block
- 11) Patient weight/BMI
- 12) Day of discharge

Subject Selection and Withdrawal

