Patients who would normally be selected to receive a TAP block, e.g., those patients with an abdominal or pelvic incision of the degree that would benefit from a TAP block, will be randomly assigned to one of three arms: TAP block via Catheter, TAP block via single shot injection of Bupivacaine, TAP block via single shot injection of Exparel. Patients may elect not to have a TAP block performed. Patients with indwelling TAP block catheters may at any time elect to have their TAP block catheters removed prior to the completion of 72 hrs. of treatment.

E2.a Inclusion Criteria

- i Participants will have signed a informed consent.
- ii Participants will be 18 years or older
- iii Scheduled for open abdominal surgery
- iv American Society of Anesthesiologists physical status (ASA) 1-3

E2.b Exclusion Criteria

- i Participants are not able to understand or provide written informed consent, or for children, are unable to assent.
- ii The research team deems that the participant may not be able to follow the study protocol.
- iii Complicated history of chronic opioid use
- iv Allergy to local anesthetics
- v Contraindication to regional nerve block (bleeding disorder, sepsis or infection at site)

- vi BMI >40 because of difficulty in placing the catheter
- vii Pregnancy
- viii Complicated history of chronic opioid use including the daily use of opioids for a period of greater than 2 weeks prior to surgery

E2.c Ethical Considerations

This study will be conducted following all local laws and regulations in the conduct of research, as well as the International Conference on Harmonisation Good Clinical Practice Guidelines. These guidelines provide a unified standard for designing, conducting, recording, and reporting trials that involve the participation of human subjects.

In addition, this study will be reviewed and approved by appropriate Institutional Review Boards prior to the initiation of any study procedures. Any modifications to this protocol will be submitted to and approved prior to submission to the appropriate Institutional Review Board(s) prior to initiation unless implementation is required to avoid an apparent immediate hazard for subjects. The protocol will undergo continuing review and approval by all IRB's providing ongoing oversight of the study.

E2.d Subject Recruitment Plans and Consent Process

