- Tingling of the fingers or toes
- Headache
- Itching
- Back pain
- Retention of urine or low urine output
- Dizziness
- Decreased touch sensation
- Anxiety
- Chest pain
- Low blood potassium
- Shortness of breath
- Muscle cramps
- Urinary tract infection

The following are side effects have been seen with Exparel®

- Nausea
- Constipation
- Vomiting
- Fever
- Dizziness
- Swelling of the arms or legs
- Anemia (including post-operative or due to bleeding)
- Low blood pressure
- Itching
- Rapid heartbeat
- Headache
- Insomnia
- Muscle spasms
- Back pain
- Sleepiness
- Procedure pain

Potential psychological risks include:

Catheter leakage at insertion site may cause dissatisfaction in that specific study arm. Also leakage may cause perceived risk of catheter dysfunction to the patient. Because leakage can occur in a fully functioning catheter this may influence patients reported post-op pain response. Also, due to the slightly increased risk of infection in the catheter group, any signs of infection would cause significant dissatisfaction in that specific arm. In addition, the visual sight of catheters along with a pump may cause the patient anxiety along the feeling of additional tubes preventing daily activity. This will be minimized by

maintaining a clean dressing over the catheter site and the use of a fanny pack the patient wears at their waist side that will contain the OnQ® infusion system.

Potential social risks include:

There is a possible social risk of embarrassment or reputational standing while responding to questionnaires or interviews.

Using trained interviewers and maintaining your records in locked cabinets or secure computer files will minimize this risk.

ii Benefits

The benefits that the subject may get from being in this study are improved post-operative pain response and quicker recovery time following surgery. A patient with improved post-operative pain will be at lower risk for pulmonary infection and circulatory issues because they will ambulate sooner along with decreased degree of pulmonary atelectasis. Decreased dependence on narcotics will also lead to faster recovery of bowel function. This overall will lead to increased patient satisfaction and earlier discharge from the hospital.

Early Withdrawal of Subjects

Subjects may be withdrawn for the following reasons:

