F3.d Data Collection Procedures for Adverse Events

Please see Attachment L2 for data collection form. All adverse event data will be entered into Oncore ERM.

F3.e Reporting Procedures

Serious Adverse Events and adverse events that meet "severe" criteria must be directly reported within 24 hours to the Principal Investigator, and the IRB.

[name] M.D.
[contact]
[contact]
Department of Anesthesiology
Midwestern Regional Medical Center
Zion, IL

Other adverse events must be entered within 7 days of collection into the Oncore ERM.

F3.f Post-study Adverse Event

Serious Adverse Events and adverse events that meet "severe" criteria must be directly reported within 24 hours to, the Principal Investigator and the IRB.

[name] M.D.
[contact]

[contact]
Department of Anesthesiology
Midwestern Regional Medical Center
Zion, IL

Other adverse events must be entered within 7 days of collection into the Oncore ERM.

F3 Study Outcome Measurements and Ascertainment

G Statistical Plan

Interim Monitoring and Early Stopping

The Principal Investigator will utilize the Oncore ERM study management system to monitor the study.

The study may be stopped early for the following reasons:

- withdrawal of funding
- safety issues
- drug has been proven effective and no further testing is needed

Analysis Plan

The study is a prospective, randomized, open, active controlled clinical trial. Effectiveness of the Continuous TAP (CTAP) via the ON-Q[®] Pain Management System will be evaluated and compared to single shot techniques with respect to reductions in postoperative opioid consumption over the first 72 hours postoperatively. Secondary outcomes including hospital length of stay (LOS), time in PACU, pain at rest and with activity, return of bowel function, and incidence of opioid related side effects will also be evaluated.

The aims of this study are to compare the efficacy of continuous TAP block via ON-Q[®] system versus that of single injection techniques for TAP block regarding opioid reduction among patients undergoing major abdominal surgery. It is hypothesized that a continuous TAP block technique reduces pain, the need for opioids as well as the expected length of stay relative to those resulting from those subjects receiving a single TAP injection of Exparel (liposomal Bupivacaine) or single TAP injection of Ropivacaine to treat postoperative pain.

Study success criteria:

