Patient characteristics and outcomes data will be summarized by cross-tabulation (categorical variables), quartiles (median, ordinal variables), and mean and standard deviation (continuous variables). Comparisons between groups will use Chi-square test or Fisher's exact test as appropriate for categorical variables and t-test or Wilcoxon rank-sum test as appropriate for continuous variables.

Analyses of primary outcome will examine differences in mean opioid consumption between the single shot TAP group and the Exparel TAP group. Analyses of secondary outcomes will examine differences in mean opioid consumption between the single shot TAP group and continuous TAP group. Treatment groups will be compared using a

student's t-test if data are normal distributed or Wilcoxon rank-sum test if not normal distributed.

The differences in mean opioid consumption across three groups (single shot TAP, continuous TAP, and Exparel TAP) will be examined with a test of means between groups using one-way analysis of variance (ANOVA). A comparison between continuous TAP and Exparel TAP will be performed. A t-test will be used if the observations in each trial arm are normally distributed; if non-normally distributed, then rank-based methods such as Wilcoxon rank-sum test will be employed.

All tests will be two-sided.

The overall incidence of serious adverse events and adverse events and number and proportion of patients reporting such events will be summarized by treatment group. Adverse events will be tabulated and summarized by the number and percentage of subjects who experienced the event.

Missing Outcome Data

Analysis will be conducted as described in prior section. Missing data will not be included in the analysis; however, may lead to an increase in patients recruited into one or more study arms.

Unblinding Procedures

This study is not blinded because it will be obvious to all care givers whether or not the patient received a continuous block with catheters or not.

H Data Handling and Record Keeping

Confidentiality and Security

Data will be collected on the data collection forms located in Attachment L9 and entered into the Oncore ERM study management system.

Data collection forms will be stored at each respective study site within a locked cabinet in a locked research office.

The Oncore ERM study management system is a secure web-based management system that is password-protected. Access to data is role-specific.

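### Leaving missing opioid totals out and recruiting substitutes conflicts with intention to treat, and no rule covers patients discharged before 48 h or 72 h

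*Combined protocol and SAP*

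**What the plan says.** **Outcome window.** Section C, Primary Aim, concerns narcotic use "required over 48 hrs. in the continuous catheter TAP block arm vs. the single shot Bupivacaine TAP arm", and likewise for Exparel against single shot. The Secondary Aim adds "narcotic requirements at other endpoints such as 24 hrs and at 72 hrs". Parameters Measured (section E) lists "Total Post-operative Narcotic Requirements over at 24, 48 and 72hrs". The Analysis Plan in section G instead speaks of "reductions in postoperative opioid consumption over the first 72 hours postoperatively".

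**Who enters.** Subject Selection and Withdrawal opens with "Patients who would normally be selected to receive a TAP block, e.g., those patients with an abdominal or pelvic incision". The criteria in E2.a and E2.b require open abdominal surgery but say nothing about expected stay.

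**What is recorded.** The form in section L has opioid totals for PACU and POD 0, 1, 2 and 3, with no entry for use after discharge. Day of discharge is a listed parameter.

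**Missing outcomes.** Section G, Missing Outcome Data: "Missing data will not be included in the analysis; however, may lead to an increase in patients recruited into one or more study arms". The Statistical Analysis Plan in the same section commits to intention to treat with every randomised participant. Where endpoints cannot be evaluated, it adds a per-protocol analysis and an analysis of non-evaluation, for which it gives no method.

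**Expected effect on stay.** E2.f, Benefits, says of better pain control and less narcotic use: "This overall will lead to increased patient satisfaction and earlier discharge from the hospital". The Analysis Plan hypothesises that continuous TAP "reduces pain, the need for opioids as well as the expected length of stay" relative to both single-injection arms, and length of stay is a secondary outcome.

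**The concern.** A cumulative total over a fixed window can be observed only while someone is recording. If recording stops at discharge and discharge comes before 48 h or 72 h, the analyst must choose how to treat that patient. The plan does not name the choice. Its only general rule is to leave missing data out and, if wanted, recruit more.

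On the protocol's own reasoning the loss would not be random: good analgesia lowers opioid use and brings discharge forward. Whether the outcome is seen then depends on both treatment and outcome. A substitute restores the patient count but not the randomised comparison, because the patient who left is still absent. The trial is also described as open, so a choice left until the data are in hand could be made with the arms known.

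**Working it through.** **1. The two rules side by side.** Intention to treat keeps all randomised participants. The Missing Outcome Data rule removes those without an outcome. A patient with no 48 h total cannot satisfy both, and the plan does not say which rule prevails.

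**2. The plan's own sample size.** Inputs from Sample Size: means 4.1 and 2.4 mg, SD 3 for sizing, two-sided 0.05, 80% power.

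n = 2 × 3² × (1.960 + 0.842)² / 1.7² = 48.9, so 49 per arm. The stated figure reproduces by the normal approximation (the exact t calculation gives 50).

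**3. Power if loss is unrelated to outcome.** Exact t, difference 1.7, SD 3, starting from the planned 53 per arm:
- no loss: 53 per arm, 82.4%
- 10% loss: 53 × 0.9 = 47.7, so 47 per arm, 77.6%
- 20% loss: 53 × 0.8 = 42.4, so 42 per arm, 72.8%

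**4. Distortion if the loss is selective.** The documents give no stay distribution, so the loss fractions are assumptions. I take gamma-distributed use with the plan's means and SDs: 4.1 (SD 3) for single shot and 2.4 (SD 1.3) for Exparel. The Background and Rationale sections give the same 2.4 and 1.3 for the catheter arm, so the arithmetic carries over to that contrast.

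Shape k = (mean/SD)², scale = SD²/mean. Single shot: k = (4.1/3)² = 1.868, scale 9/4.1 = 2.195. Exparel: k = (2.4/1.3)² = 3.408, scale 1.69/2.4 = 0.704.

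If the lowest fraction L of users is dropped, with q the L-quantile and F(k+1) the gamma distribution function with shape k+1 and the same scale, the remaining mean is

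mean × [1 − F(k+1)(q)] / (1 − L).

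| Lost: control / Exparel | Control mean | Exparel mean | Difference (true 1.70) |
|---|---|---|---|
| 0% / 10% | 4.10 | 2.59 | 1.51 |
| 0% / 20% | 4.10 | 2.77 | 1.33 |
| 5% / 10% | 4.29 | 2.59 | 1.70 |
| 5% / 20% | 4.29 | 2.77 | 1.52 |
| 10% / 20% | 4.48 | 2.77 | 1.71 |
| 10% / 10% | 4.48 | 2.59 | 1.90 |

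As a share of 1.70 the extremes are (1.33 − 1.70)/1.70 = −22% and (1.90 − 1.70)/1.70 = +12%. Dropping low users raises both means. The control arm is more spread out, so the same fraction lost raises its mean further. That is why equal loss widens the gap and one-sided loss narrows it.

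The near-cancellation at 10%/20% depends on the SDs. If Exparel use also had SD 3, which the plan uses only for sizing, the difference would read 1.51 there, 1.63 at 5%/10%, 1.13 at 0%/20% and 1.82 at 10%/10%. The direction still varies.

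**5. If the total is cut at discharge instead.** When a fraction p of an arm leaves early and each such patient uses a further u mg before the window closes, that arm's mean is understated by p × u. More early leavers in the better arm would then exaggerate its advantage, whereas dropping low users from that arm alone shrinks it. The documents give neither p nor u, so I put no figure on this.

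**The case against.** **A reader might infer that early leavers are certainly lost.** The documents do not say so. No section classes discharge as missing data or lists it as a reason for withdrawal. The rationale for the outcome measures equates narcotic requirements with IV PCA use, so a total to discharge could be taken as complete. This stands, and it is why the point says such patients may be dropped or truncated. It does not remove the problem: the truncated reading is unstated too, and it distorts in its own way.

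**A reader might infer that the result will be biased against the better technique.** The table does not support a fixed direction. Two cases with more loss in the Exparel arm leave the difference almost unchanged. Removing exactly the lowest users is also a worst case, and a looser link between use and discharge gives smaller shifts. The 72 h window was not modelled.

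**A reader might infer that the defect lies in eligibility and that an expected-stay criterion would cure it.** It would not. Actual discharge follows randomisation and is expected to depend on treatment, and such a criterion narrows the population.

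**Few patients may leave before 48 h.** Open abdominal surgery, PCA on the floor and data fields to POD 3 suggest an inpatient population. Nothing in the documents supports 10% to 20% leaving that early. The 72 h total is more plausibly exposed, and a patient who leaves between 48 h and 72 h still has complete 24 h and 48 h totals.

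**Post-discharge collection may be described elsewhere.** The form is a template open to additions, and attachments L1 and L9 are cited but not seen under those labels. The absence is therefore of any description in the text available.

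**The plan already promises intention to treat and an analysis of non-evaluation.** It does, but with no method given, and the missing-data rule contradicts the first promise.

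**Conclusion.** The point holds in limited form. The conflict between the missing-data rule and the intention-to-treat commitment is on the page and needs no assumption. That early discharge brings it into play is a well-founded risk, not an established fact: it rests on the protocol's own expectation of earlier discharge, on a form with no post-discharge entry, and on the lack of any rule for this case.

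For the contrast used for sizing, the expectation of earlier discharge in the Exparel arm comes from the Benefits text. The Analysis Plan's hypothesis about stay concerns the catheter arm.

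The size is unknown. Under the worst-case gamma model with the plan's means and SDs, a true 1.70 mg could read from about 1.33 to 1.90 mg, in either direction or hardly changed. This should be settled before enrolment, because opioid use after discharge may not be recoverable later. It is not grounds for calling the design unsound.

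**What to change.** Replace the rule in Missing Outcome Data and align it with the Statistical Analysis Plan:

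- All randomised patients, including those discharged early, stay in the primary analysis in their assigned arm. Extra recruitment does not remove or stand in for anyone already randomised.
- Record the time of discharge, not only the day. For patients who leave before 48 h or 72 h, complete opioid use to both time points from discharge medication and one follow-up call, converted to hydromorphone equivalents by a table fixed in advance.
- Where the total is still incomplete, use one prespecified primary method, for example multiple imputation of the interval after discharge.
- Add two sensitivity analyses: post-discharge use counted as zero, and use continued at the last in-hospital rate.
- Report by arm how many patients left before 48 h and before 72 h.

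The 48 h window in the Primary Aim and the 72 h window in the Analysis Plan must also be reconciled, since the choice decides how many patients this affects. An expected-stay criterion is not needed for this fix.

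The cost is one form field, a call for what may be a few patients, and a short rewrite of the plan. The drawback is some recall error in reported home use, which the sensitivity analyses help to judge.
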